#### where:

- Attendance is the fraction of sessions attended.
- $\alpha$  and delta are regression constants.
- $S_i$  is a binary indicator of treatment assignment, set to 1 if participants have been assigned to treatment, and 0 else. This is our instrumental variable.
- Predicted attendance is the fitted value of attendance from the first stage regression.
- $Y_{it-1}$  is participant I's baseline score for the outcome measure.
- $X_i$  is a vector of participant level characteristics.
- $\epsilon_i$  is a Huber white robust standard error.
- *tau*it is a Huber white robust standard error.
- d. Schwartz Rounds will be considered acceptable by the intervention group. We will measure this with the IPE as set out below.

# **Exploratory Analysis**

In addition to the primary and secondary analyses outlined above, we will seek to explore whether there are any associations in our data between GHQ-12 scores and the following variables – local authority, team, role, length of time in post, gender, ethnicity and age. We will also look at any differences based on face-to-face or virtual attendance. This analysis is only exploratory, and the study is not powered for this.

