As set out in the previous protocol, we initially planned to work with six local authorities in total, with all of them providing Schwartz Rounds face-to-face. We expanded the study to include five additional local authorities in order to increase the sample size and the chances of avoiding a false negative result (i.e., failing to identify a positive effect on staff levels of stress caused by Schwartz Rounds). The original six authorities are referred to as phase one (of the trial), and the additional five authorities as phase two (of the trial). The plan at the outset, at the point when the five new authorities were recruited, was that they would also provide face-to-face Schwartz Rounds for their staff, in the same way the authorities in phase one had done. However, due to the Covid-19 pandemic and associated lockdowns and social distancing requirements this was not possible. Therefore, the phase two authorities will deliver virtual Schwartz Rounds (also called Team Time) instead.

Although there are no published studies that we could find which compare the effectiveness of face-to-face Schwartz Rounds with virtual Schwartz Rounds, there are studies of face-to-face counselling compared to online counselling, which tend to find similar levels of effectiveness (e.g., Barak et al, 2008; Stefanopoulou et al., 2018). This could suggest that virtual Schwartz Rounds may have a similar effect to that of face-to-face Schwartz Rounds (albeit we intend to consider this empirically as part of our exploratory analysis).

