# Design

The overall study design is an individually randomised control trial with group delivery of the intervention. It is a two-arm study, with an intention-to-treat intervention group and a waiting-list control, with the aim of assessing the effectiveness of Schwartz Rounds within children's social care in relation to the psychological well-being of staff.

Trial Type and Number of Arms		Randomised control trial with two arms (intention-to-treat and waiting-list control)	
Unit of Randomisation		Individual members of staff	
Stratification Variables (if applicable)		Phase (one or two)	
Primary Outcome	Variable	Psychological well-being of staff	
	Measure (instrument, scale)	GHQ-12	
Secondary Outcome(s)	Variable(s)	Sickness-related absence	
	Measure(s) (instrument, scale)	Self-report	

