#### Randomisation

A researcher not otherwise involved in the study will use staff lists provided by the LAs to create equal-sized intervention and waiting-list-control groups, with staff randomly allocated to each group.

To achieve this, each LA will provide a pseudonymised list of staff working in children's services (e.g., based on employee numbers). Using Excel's randomisation feature a random number will be generated for each employee, the list will then be sorted from smallest to largest, and then split in half at the median value to create two equal sized groups (plus or minus one, if the list contains an odd number of staff; Zelen, 1979). Each LA will then be given a list of staff in each group, which they can re-identify and circulate, so as to ensure that members of staff know which group they are in (this information will not be shared with staff until after the T1 survey has been closed).

The control group will be asked not to attend Schwartz Rounds during the trial period but will continue to receive 'business as usual' support from their authorities. The intervention group will also continue to receive 'business as usual' support but will also be invited to attend Schwartz Rounds (whether virtually or face-to-face). For social workers, 'business as usual' support will likely include monthly one-to-one supervision with a line manager. In some sites, this may also include group supervision, reflective practice groups or other group-based interventions. Some sites may also provide staff with counselling services where this is required. For non-social work staff, 'business as usual' support may include some or none of these elements. We will ask staff about what other support they have available and what other support they have accessed as part of the T2 survey.

Direct contamination (by members of the control group attending Schwartz Rounds) will be measured via sessional feedback questionnaires. The extent and significance of indirect contamination (by members of the intervention group talking about the intervention outside of rounds) will be explored via focus groups at T2.

Analysts will be blinded to group allocation in relation to GHQ-12 and group-level absence data.

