# **Sample Size Calculations**

		MDES (Proportion of a Standard Deviation)
MDES		0.23
	Child	n/a
Baseline/Endline Correlations	Family	n/a
	Social Worker	0.33
	Family	n/a
Intracluster Correlations (ICCs)	Social Worker	n/a
	Team	n/a
Alpha		0.05
Power	0.8	
One-sided or Two-sided?	One-sided	
Level of Intervention Clustering	Individual	
Average Cluster Size		n/a
Sample size of children's services	Intervention	238
staff, including social workers and others (without drop out	Control	238
adjustment)	Total	476
Sample size of children's services	Intervention	476
staff, including social workers and others (adjustment for 50% lost to follow-up)	Control	476
	Total	952
Sample size of children's services staff, including social workers and	Intervention	952
others (adjustment for 75% lost to	Control	952
follow-up)	Total	1904

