#### Where:

- $Y_{it}$  is the level of an outcome measure observed by participant I at time t (the T2 survey).
- α is a regression constant.
- $S_i$  is a binary indicator of treatment assignment, set to 1 if participants have been assigned to treatment, and 0 else.
- $Y_{it-1}$  is participant I's baseline score for the outcome measure.
- $X_i$  is a vector of participant level characteristics (gender, age, ethnicity, phase 1 or phase 2).
- $\epsilon_i$  is a Huber white robust standard error.

Where participants have T2 data but not T1 data,  $Y_{it-1}$  will be inputted as 0, and a binary variable contained within the vector X denoting that baseline data are missing will be set to 1 (else 0).

Secondary analysis will be considered using matched exclusion. For this analysis the model used will be identical to the main model, with the data used for the model having been subject to exclusion. Participants for exclusion will be matched on characteristics contained within X and on their baseline GHQ-12 data.

The sample size for the RCT was based on a one-sided hypothesis and this will be reflected in the reporting of the results of the primary analysis.

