#### **Contextual Factors Analysis**

Although the intervention will be implemented in a similar way within the phase one authorities and within the phase two authorities, each site is likely to be distinctive in some potentially important way.

There are various contextual factors that could influence the effectiveness of the treatment. The four that appear most likely in prospect are:

- Baseline GHQ-12 scores
- Level of support and enablement for staff to attend the rounds
- Workforce composition
- Delivery of the intervention face-to-face or virtually

Other unexpected factors may also influence effectiveness, such as Ofsted inspections or a high-profile incident in the authority.

We will explore these contextual factors via focus groups and interviews at T2.

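### The face-to-face versus virtual question is framed by attendance, which mixes mode with phase and self-selection; randomised effects by phase would be less biased, though they cannot isolate mode

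*Protocol*

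**What the plan says.** All references are to the protocol.

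- **Exploratory Analysis:** "We will also look at any differences based on face-to-face or virtual attendance". No model, population or comparator is named. The section labels the work exploratory and not powered. The table of changes also words it as a comparison between attending the two kinds of round.
- **Background and Problem Statement:** virtual rounds may have a similar effect to face-to-face rounds, "albeit we intend to consider this empirically as part of our exploratory analysis". The table of changes explains that the primary hypothesis was reworded because the pandemic may have raised stress overall.
- **Intervention and Theory of Change:** six phase one authorities hold at least six face-to-face rounds in 2019. Five phase two authorities hold at least four virtual rounds between November 2020 and April 2021. Attendance is optional in both formats, and the formats differ in group size, length and focus.
- **Randomisation:** each authority's staff list is "split in half at the median value to create two equal sized groups". The Design table gives phase as the stratification variable.
- **Primary Analysis:** phase enters as a covariate; there is no treatment-by-phase term.
- **Contextual Factors Analysis:** baseline GHQ-12 and mode are among four factors thought likely to influence effectiveness. The method is: "We will explore these contextual factors via focus groups and interviews at T2".
- **Implementation and Process Evaluation:** interviews are planned in two phase one authorities that later switched to virtual rounds.

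**The concern.** The protocol asks whether virtual rounds work as well as face-to-face ones, which is a question about effects. The only quantitative analysis it offers is worded by mode of attendance. Comparing people who attended in 2019 with people who attended in 2020-21 sets different authorities against each other, before and during a pandemic, among staff who chose to come. If stress rose for everyone, virtual rounds would look worse even if both formats worked equally well.

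The label exploratory warns of imprecision, not of bias: a larger sample would only tighten the interval around the wrong value. The design already contains a better contrast, because each phase has its own randomised control group. At stake is what the report says about virtual delivery.

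**Working it through.** **Inputs.** From Sample Size Calculations: MDES 0.23 SD, alpha 0.05, power 0.8, baseline/endline correlation 0.33, and 238 per arm (476) before drop-out adjustment. On sidedness: "The sample size for the RCT was based on a one-sided hypothesis". The documents do not give the split of respondents between phases (assumed 6:5, the ratio of authorities; range 50:50 to 80:20), the size of any phase shift (assumed 0 to 0.5 SD), or the share of the intervention arm attending (assumed half).

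**Step 1: the plan's own figure.** n per arm = 2(1.645 + 0.842)² / 0.23² = 234, against 238 stated. At 238 per arm the MDES is 2.487 × √(2/238) = 0.228, which rounds to 0.23. The stated size is therefore reproduced without the 0.33 correlation; using it would give 209.

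**Step 2: what each comparison estimates.** Let δ be a shift in T2 GHQ-12 between phases that has nothing to do with treatment.

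- Virtual attendees minus face-to-face attendees = difference in effects + δ + difference in who attends.
- (Intervention − control in phase two) − (intervention − control in phase one) = difference in effects of assignment. δ cancels, and selection into attendance does not enter.

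If T1 scores moved by the same δ and are adjusted for, the attendee comparison keeps about (1 − 0.33)δ = 0.67δ. For δ = 0.1, 0.3 and 0.5 that leaves 0.07, 0.20 and 0.34 SD. This is plausible, because the Timeline puts phase two T1 in October and November 2020, within the pandemic.

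**Step 3: simulation.** 2,000 runs with 476 analysed, equal phases, a true effect of −0.23 SD in both modes, half of the intervention arm attending at random (so no self-selection), and a shift at T2 only. Robust standard errors, 5% two-sided tests.

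| Assumed shift (SD) | Attendee mode difference | False positives | Treatment-by-phase term | False positives |
|---|---|---|---|---|
| 0 | 0.00 | 6% | 0.00 | 5% |
| 0.1 | 0.10 | 9% | 0.00 | 6% |
| 0.2 | 0.21 | 23% | 0.00 | 5% |
| 0.3 | 0.29 | 38% | −0.01 | 6% |
| 0.5 | 0.50 | 81% | 0.00 | 4% |

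**Step 4: precision of the randomised contrast.** A 6:5 split of 238 per arm gives about 130 and 108 per arm. The variance of each phase effect is 2(1 − 0.33²)/n.

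- Phase one: 2 × 0.8911/130 = 0.0137; SE 0.117; 95% CI ±0.23 SD.
- Phase two: 2 × 0.8911/108 = 0.0165; SE 0.128; 95% CI ±0.25 SD.
- Interaction: √(0.0137 + 0.0165) = 0.174; 95% CI ±0.34 SD.

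Over splits from 50:50 to 80:20 the interaction SE runs from 0.173 to 0.216, so ±0.34 to ±0.42 SD. Power to detect a 0.23 SD difference between phases is 17% to 38%, depending on split, sidedness and use of the correlation.

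**The case against.** The strongest reply is that the criticised analysis is inferred. The sentence in Exploratory Analysis names no model and does not exclude controls, the Background speaks of a similar effect, and model detail for an exploratory analysis can sit in a statistical analysis plan that is not shown. This stands in part: a reader might infer that the protocol fixes an attendees-only comparison, and it does not. But two places word the comparison by attendance and neither mentions controls, so the wording points to the biased analysis.

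Four further limits stand:

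- A reader might infer that the aliasing of mode with phase arises from the analysis. It comes from the design, and the interaction does not remove it: period, authority and number of rounds remain as possible modifiers of the effect.
- A reader might infer that the primary analysis is faulty because it assumes one effect. It is not: phase is adjusted for, and the pooled intention-to-treat effect is a valid average over phases.
- Contextual Factors Analysis promises only to explore, and does not claim to estimate effect modification. A treatment-by-baseline term is an addition, not a correction.
- The interviews in two authorities that used both formats give evidence on mode that is not aliased with authority, though it is still aliased with time.

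The protocol also already concedes low power, and the better contrast will seldom settle the question.

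**Conclusion.** The point holds in limited form. Read naturally, the planned comparison by mode of attendance would return the phase shift in stress plus self-selection along with any mode difference. The bias from the shift is roughly the size of the shift: 0.1 to 0.5 SD on assumed values, against an MDES of 0.23, and about two thirds of that if T1 moved equally and is adjusted for. The documents give no figure for the shift, so no single value should be quoted as the error.

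The randomised contrast by phase is free of both problems, subject to loss to follow-up. Its interval of about ±0.34 SD rests on 476 analysed, the 6:5 split and r = 0.33. It answers whether the effect differed between phases, not whether mode caused the difference. The consequence is confined to what the report says about face-to-face versus virtual delivery; the primary result does not change.

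**What to change.** - In Exploratory Analysis, replace the comparison by attendance with the intention-to-treat effect and 95% CI within each phase, plus a treatment-by-phase interaction added to the primary model (estimate and 95% CI).
- State that the interaction removes the main effect of phase and self-selection into attendance, but cannot separate mode from period, authority or number of rounds, so it is a phase difference in effect.
- Optionally add a treatment-by-baseline GHQ-12 term, since Contextual Factors Analysis names baseline GHQ-12 as a likely influence and gives it only a qualitative method.
- Keep the planned interviews as the qualitative evidence on mode.

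The cost is one or two terms in an existing model and no new data. The drawback is wide intervals, so the results should be labelled exploratory, and a non-significant interaction should not be read as showing that the formats are equivalent.

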#### **Contextual Factors Analysis**

Although the intervention will be implemented in a similar way within the phase one authorities and within the phase two authorities, each site is likely to be distinctive in some potentially important way.

There are various contextual factors that could influence the effectiveness of the treatment. The four that appear most likely in prospect are:

- Baseline GHQ-12 scores
- Level of support and enablement for staff to attend the rounds
- Workforce composition
- Delivery of the intervention face-to-face or virtually

Other unexpected factors may also influence effectiveness, such as Ofsted inspections or a high-profile incident in the authority.

We will explore these contextual factors via focus groups and interviews at T2.

# **Implementation and Process Evaluation**

The implementation and process evaluation will seek to address the following questions:

- Is it feasible to implement Schwartz Rounds (face-to-face and online) in children's services?
- What adaptations, if any, are made to the intervention as it is implemented in children's services?
- How do social workers and other members of staff view the experience of attending Schwartz Rounds?
- For members of staff in the intervention group who do not attend, what reasons do they give for their non-attendance?
- For members of staff who attend irregularly (between 1-3 Schwartz Rounds), what reasons do they give for their irregular attendance?
- For members of staff who attend regularly (4+ Schwartz Rounds), what reasons do they give for their regular attendance?
- How do key informants within children's services (e.g., Assistant Directors, Principal Social Workers, Heads of Service, facilitators and Practice Leads) view the intervention?
- What impact do attendees think Schwartz Rounds have had on their psychological wellbeing?
- What impact do attendees think Schwartz Rounds have had on their work with children and families?

The primary methods for addressing these research questions will be interviews (with key informants) and focus groups (with members of staff). The data gathered from these methods will be supplemented via sessional feedback questionnaires, completed by participants at the end of each Schwartz Round.

The level of fidelity in each local authority will be assessed jointly by the evaluation and the intervention team, based on Maben et al.'s (2018) nine CMOs. Experienced trainers from the Point of Care Foundation will observe at least one round or virtual round in each site. Researchers from the evaluation team will do the same. The researchers and the experienced trainers will discuss their observations of each site and agree whether they have successfully implemented the intervention.

During both phases of the project, at least two Schwartz Rounds will be observed at each site, one by the Point of Care Foundation and one by a researcher from the evaluation team. Research observations will be recorded in hand-written notes, with reference to the nine CMOs identified by Maben et al. (2018).

Sessional feedback questionnaires will be handed out on paper to every attendee at a face-to-face Schwartz Round and distributed via Qualtrics to each attendee at a virtual Schwartz Round. These forms are used widely in Schwartz Round studies and ask people to report their subjective experience of having attended. We will also use these as a record of attendance, by asking participants to include their initials and day and month of birth. We will also ask each LA for a record of how many people attended each session. The paper forms will be collected back in at the end of each round and collected from each site by a member of the research evaluation team. The data from the forms (both paper and online) will be entered into SPSS. The SPSS database will be stored securely on a Cardiff University computer. Paper copies are kept in a secure locked cupboard at Cardiff University, accessible only to members of the evaluation team.

Focus groups and interviews will be held for each site, either in the local authority offices or online. Interviews and focus groups will be conducted and facilitated by members of the evaluation team. They will be audio recorded using digital Dictaphones. Recordings will be uploaded to a secure Cardiff computer and deleted from the Dictaphone as soon as reasonably possible. Interviews and

focus group recordings will then be transcribed and analysed using Nvivo, based on a coding framework developed from the relevant research questions.

To help compare the experience of attending and providing face-to-face and virtual rounds, we will also conduct interviews with key informants and staff members in two phase one authorities (who provided face-to-face rounds previously and during the Covid-19 associated lockdown have switched to virtual rounds).

#### **Cost Evaluation**

An economic evaluation will be incorporated into the trial design for the collection of both costs and outcomes data at T1 and T2. A cost-effectiveness analysis (CEA) will be carried out from a social care perspective.

Costs related to the delivery of Schwartz Rounds will encompass the costs of setting-up and delivering the Schwartz Rounds intervention. These will include training costs for the Practice Lead and facilitators of the Schwartz Rounds at each local authority, venue and catering costs for each face-to-face Schwartz Round and staff costs including time spent attending a Schwartz Round as well as time spent on preparation and administrative tasks in-between each round.

Direct and indirect costs of the intervention will be gathered from each local authority:

- The direct cost of the contract with the Point of Care Foundation is £5,000 per authority.
- Data on room use and catering costs will be collected from each local authority conducting face-to-face Schwartz Rounds.
- Staff time for attendance will be calculated based on sessional feedback questionnaires.
- Staff time for preparation and administration will be collected from each local authority, via interviews with facilitators, Practice Leads and administrators.
- We will also consider what different costs might be associated with virtual rounds, compared to face-to-face rounds e.g., no money required for food, additional costs for IT equipment.

In addition, sickness-related absences will be tracked at the level of the individual social worker to calculate any potential savings resulting from the intervention. This will be based on knowledge of the grade of each social worker randomised in the trial applied to administrative data on sickness-related absence and retention collected from each local authority. This data will be used to calculate any potential savings resulting from the intervention.

The results of the CEA will be expressed in an incremental cost per unit reduction in the GHQ-12 score. The impact of uncertainty on the CEA results will be quantified by carrying out a probabilistic sensitivity analysis and summarising the results using cost-effectiveness acceptability curves.

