#### Differences:

Schwartz Rounds and Team Time differ because Team Time is aimed at smaller groups of people, not the whole organisation. There are fewer story tellers, and a shorter timeframe for the session overall, although they may be run more frequently. The focus of the stories is on current experiences, rather than past events. Team Time relies on virtual forms of communication without physical contact and interaction, including the sharing of food (which is a key feature of Schwartz Rounds). There is typically less preparation time involved with Team Time, and other techniques may be used such as mindful breathing.

[figure not shown]
You can read more about Team Time on the Point of Care Foundation's website here.

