#### **Data Protection**

We will only collect and process data in order to address our research questions. In all circumstances, the identities of individuals taking part in the study and the data they provide will be kept confidential and will only be used for research purposes. Participants will be informed of their right not to take part in the study, either by not attending Schwartz Rounds or by attending without taking part in data collection activities.

Data will be processed only when the data subject has given consent to the processing of his or her personal data for the specific purpose of conducting this trial.

All data collected will be stored securely on Cardiff University computers.

Cardiff University's research data protection notice can be read – here.

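### Attendance time in the cost-effectiveness analysis rests on feedback forms that attendees may decline, and the per-session head count requested from each authority is given no role in it

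*Protocol*

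**What the plan says.** The Cost Evaluation section includes in the cost of the intervention "staff costs including time spent attending a Schwartz Round as well as time spent on preparation and administrative tasks in-between each round". For the attendance part it states: "Staff time for attendance will be calculated based on sessional feedback questionnaires". It names no second source and no correction for missing forms. The result is to be an incremental cost per unit reduction in GHQ-12 score, with a probabilistic sensitivity analysis. The section also says that differences in cost between virtual and face-to-face rounds will be considered.

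Three other parts of the protocol bear on this source.

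- **Implementation and Process Evaluation.** The feedback forms double as the attendance register: "We will also use these as a record of attendance, by asking participants to include their initials and day and month of birth". They are on paper at face-to-face rounds and sent through Qualtrics for virtual ones. The same paragraph adds: "We will also ask each LA for a record of how many people attended each session".
- **Data Protection.** Staff may opt out "either by not attending Schwartz Rounds or by attending without taking part in data collection activities". It also says: "Data will be processed only when the data subject has given consent to the processing of his or her personal data".
- **Differences** (virtual against face-to-face). Of virtual sessions it says: "There are fewer story tellers, and a shorter timeframe for the session overall". No duration is given. The health-care description quoted under Intervention and Theory of Change puts a round at 1 hour.

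**The concern.** A person who attends but returns no usable form has still spent paid time at the round. If hours are built up from forms alone, that time drops out of the cost. The error runs one way, because the opt-out rule lets forms fall short of attendance and nothing in the protocol would lead them to exceed it. Cost per unit reduction in GHQ-12 would then look better than it is. The probabilistic sensitivity analysis would not correct this unless undercounting is one of its parameters. Otherwise it spreads uncertainty around a centre that is too low.

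There is a second, weaker worry. The reminder and hand-back on leaving the room, described under Ethics & Participation, suit a paper form, and no matching step is stated for the online form. Return rates could therefore differ by mode, which would blur any look at cost by mode. A count of forms also gives people and not hours, and the cost section does not say what session length will be applied to either mode.

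**Working it through.** The protocol gives no attendance figure, return rate, staff-time figure or total cost, so there is no stated result to reproduce. The arithmetic below shows how the error scales. Every value of *r* and *s* is an assumption.

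**Definitions**

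- *r* = usable forms returned / people attending
- *s* = attendance time as a share of the true total intervention cost

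**Step 1: attendance component.** Hours captured = true hours × *r*, so the shortfall is 1 − *r*. Restoring the true hours means multiplying by 1/*r*.

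- *r* = 1.0: shortfall 0%
- *r* = 0.9: shortfall 10%, factor 1/0.9 = 1.11
- *r* = 0.7: shortfall 30%, factor 1/0.7 = 1.43
- *r* = 0.5: shortfall 50%, factor 1/0.5 = 2.00

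**Step 2: total intervention cost.** Only the attendance component is affected. Training, the provider contract (£5,000 per authority), venue, catering, preparation and administration are not. The shortfall in total cost is *s* × (1 − *r*). For example, 0.4 × (1 − 0.7) = 0.12, or 12%.

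| | *s* = 0.2 | *s* = 0.4 | *s* = 0.6 |
|---|---|---|---|
| *r* = 0.9 | 2% | 4% | 6% |
| *r* = 0.7 | 6% | 12% | 18% |
| *r* = 0.5 | 10% | 20% | 30% |

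**Step 3: the ratio.** For a given GHQ-12 effect, and taking incremental cost to be the cost of the intervention, cost per unit reduction falls by the same percentage.

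**Step 4: mode.** The ratio of hours captured per true hour, virtual to face-to-face, is *r*(virtual) / *r*(face-to-face).

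- 0.9 / 0.9 = 1.00: no distortion between modes
- 0.7 / 0.9 = 0.78: virtual rounds look cheaper than they are, relative to face-to-face
- 0.5 / 0.9 = 0.56: the same, more strongly
- 0.9 / 0.7 = 1.29: the reverse

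The protocol does not say which of these applies.

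**The case against.** The best reply is that nothing here is shown to have gone wrong. Forms go to every attendee in both modes, with a reminder described at the end of each round, and return may be close to complete. Calculating time on the basis of the forms does not rule out scaling them to the head count, and the head count is requested just after the forms are described as the attendance record. Adjustment for missing forms might be left to an analysis plan that is not shown. This stands as a limit on the claim: the understatement is conditional on missing forms and on no scaling. It does not remove the point, because the protocol does name the source, and it gives no role to a count that does not depend on anyone filling in a form.

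A reader might infer three stronger things, none of which the protocol supports.

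- *That virtual rounds will be made to look cheaper.* No return rates are given, equal rates distort nothing between modes, and a higher online rate reverses the effect. The examples given for the look at cost by mode are food and IT equipment; no cost-effectiveness ratio for each mode is announced.
- *That full head counts are already in hand.* Authorities will be asked for them. Under Outcome measures, the protocol records that no phase one authority could supply another requested item, sickness absence by staff group. Phase one data collection is also complete according to the Timeline, so gaps may be hard to fill.
- *That virtual rounds will be costed at the wrong length.* The cost section does not say that an hour will be applied to them, and the Similarities text says sessions keep to a strict time frame, so duration should be known.

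A raw head count also has faults. It may include observers, facilitators and Practice Leads, and it cannot separate the arms, whereas the Randomisation section relies on the forms to detect control-group attendance. Nor are the forms said to record grade. These objections are sound and shape the fix.

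**Conclusion.** The point holds in conditional form. The protocol costs attendance from forms that staff may decline and assigns no role in the costing to the head count it requests. If any attendee leaves no usable form and no scaling is applied, attendance cost is too low by 1 − *r*, total intervention cost by *s* × (1 − *r*), and the cost per unit reduction in GHQ-12 is too favourable. Over the assumed ranges the effect on total cost runs from 2% (*r* = 0.9, *s* = 0.2) to 30% (*r* = 0.5, *s* = 0.6), and it is nil if every attendee returns a usable form. Unequal capture by mode is a risk of unknown size and direction. The matter is confined to the economic evaluation and is worth correcting because the bias can run only one way and is cheap to remove.

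**What to change.** Amend the Cost Evaluation section as follows.

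1. Calculate attendance hours as the authority's head count for each round × the scheduled length of that round, kept separate for face-to-face and virtual rounds. Exclude observers from the count, and exclude facilitators and Practice Leads if their time is costed separately.
2. Use the feedback forms, linked to T1 data where possible, for staff mix and to identify control-group attendees.
3. Report forms returned / head count by mode.
4. Where a head count is missing, divide the forms by the observed return rate, and vary that rate in the planned probabilistic sensitivity analysis.

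The cost is a short addition to the text, a little extra analysis work, and probably a somewhat higher and less favourable cost estimate. The head counts are already to be requested, so no new data item is needed, but their completeness is not assured, which is why step 4 is included.
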